5.4. Screen Failures

Participant Identification, Enrollment, and Screening Logs

The investigator agrees to complete a participant identification and enrollment log to permit easy identification of each participant during and after the study. This document will be reviewed by the sponsor study-site contact for completeness.

The participant identification and enrollment log will be treated as confidential and will be filed by the investigator in the study file. To ensure participant confidentiality, no copy will be made. All reports and communications relating to the study will identify participants by participant identification and age at initial informed consent. In cases where the participant is not enrolled into the study, the date seen and age at initial informed consent will be used.

Individuals who do not meet the criteria for participation in this study (screen failure) may be rescreened. A participant may be rescreened within 30 days from the previous ICF signature date.

In cases where the rescreening is considered after 30 days from the previous ICF signature date, the decision on rescreening must be taken after a discussion between the investigator and the Medical Monitor. Participants who are rescreened are required to sign a new ICF.

6. STUDY INTERVENTION

6.1. Study Intervention Administered

All eligible participants will be treated with study intervention and need to follow the dosing and toxicity management guideline described as follows. Study intervention administration must be captured in the source documents and the eCRF. Study-site personnel will instruct participants on how to store study intervention for at-home use as indicated in this protocol.

Study Intervention

Ibrutinib 420 mg (140 mg×3 capsules) orally administered daily beginning from Day 1 in Week 1 until disease progression or unacceptable toxicity.

Rituximab 375 mg/m² intravenous (IV) per prescribing information weekly for 4 consecutive weeks, followed by a second course of once-weekly rituximab for 4 consecutive weeks after a 12-week interval. Day 1 of Weeks 1 to 4 and Weeks 17 to 20 (total of 8 infusions of rituximab).

6.1.1. Ibrutinib

6.1.1.1. Dose and Administration

Ibrutinib (140 mg×3 capsules) is administered orally once daily with approximately 240 mL of water. The capsules should be swallowed whole and should not be opened, broken, or chewed.

Ibrutinib will be administered prior to rituximab when given on the same day.

The first dose will be administered at the study site on Week 1 Day 1 and subsequent dosing will occur on an outpatient basis except for PK sampling day on Week 4 Day 1.

6.1.1.2. Dose Hold, Reduction or Discontinuation of Ibrutinib

Treatment with ibrutinib should be withheld for any unmanageable, potentially ibrutinib-related nonhematological toxicity that is ≥Grade 3 in severity and any hematologic toxicity meeting the criteria in Section 6.1.1.3. Ibrutinib may be withheld for a maximum of 28 consecutive days for toxicity. Ibrutinib should be discontinued in the event of a toxicity lasting >28 days, unless reviewed and approved by the Medical Monitor.

6.1.1.3. Dose Modification for Adverse Reactions

The dose of ibrutinib should be modified according to the dose modification guidance in [Table 2](#) or [Table 3](#) if any of the following drug-related toxicities occur:

Refer to [Table 2](#)

- Grade 3 or greater neutropenia with infection or fever

- Grade 4 ANC (<500/ μ L) for >7 days
- Grade 3 thrombocytopenia (platelets <50,000/ μ L) in the presence of \geq Grade 2 bleeding events
- Grade 4 thrombocytopenia (platelets <25,000/ μ L)
- Grade 3 or 4 nausea, vomiting, or diarrhea if persistent, despite optimal antiemetic and/or antidiarrheal therapy
- Any other Grade 4 or unmanageable Grade 3 toxicity attributed to ibrutinib (except events specified in [Table 3](#))

Refer to [Table 3](#)

- Grade 2 or higher cardiac failure and Grade 3 or higher cardiac arrhythmias

For Grade 3 or 4 atrial fibrillation or persistent atrial fibrillation of any grade, consider the risks and benefits of ibrutinib treatment. If clinically indicated, the use of anticoagulants or antiplatelet agents may be considered for the thromboprophylaxis of atrial fibrillation (Section [6.5.2.3](#)).

Table 2: Ibrutinib Dose Modifications for Events not Specified in [Table 3](#)

Occurrence	Action to be Taken
First	Withhold ibrutinib until recovery to Grade \leq 1 or baseline; may restart at original dose level ^a
Second	Withhold ibrutinib until recovery to Grade \leq 1 or baseline; may restart at 1 dose level lower (ie, 280 mg/day / 2 capsules)
Third	Withhold ibrutinib until recovery to Grade \leq 1 or baseline; may restart at 1 dose level lower (ie, 140 mg/day / 1 capsule)
Fourth	Discontinue ibrutinib ^b

^a When resuming treatment, restart at the same or lower dose based on benefit risk evaluation. If the toxicity reoccurs, reduce daily dose by 140 mg.

^b If the oral ibrutinib is discontinued for toxicity, participant will end the treatment phase of the study.

Table 3: Ibrutinib Dose Modifications for Cardiac Failure or Cardiac Arrhythmias

Events	Occurrence	Action to be Taken
Grade 2 cardiac failure	First	Withhold ibrutinib until recovery to Grade \leq 1 or baseline; restart at 1 dose level lower (ie, 280 mg/day / 2 capsules)
	Second	Withhold ibrutinib until recovery to Grade \leq 1 or baseline; restart at 1 dose level lower (ie, 140 mg/day / 1 capsule)
	Third	Discontinue ibrutinib ^b
Grade 3 cardiac arrhythmias	First	Withhold ibrutinib until recovery to Grade \leq 1 or baseline; restart at 1 dose level lower (ie, 280 mg/day / 2 capsules) ^a
	Second	Discontinue ibrutinib ^b
Grade 3 or 4 cardiac failure	First	Discontinue ibrutinib ^b
Grade 4 cardiac arrhythmias		

^a Evaluate the benefit-risk before resuming treatment.

^b If the oral ibrutinib is discontinued for toxicity, participant will end the treatment phase of the study.

Refer to Section [6.5.2.1](#) for guidelines for management of ibrutinib in participants who require treatment with a CYP3A inhibitor.

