6.1.1.4. Dose Modification for Hepatic Impaired Participants

Ibrutinib is metabolized in the liver. For participants who develop mild liver impairment while on study (Child-Pugh class A), the recommended dose reduction for ibrutinib is to a level of 280 mg daily (2 capsules). Participants who develop moderate or severe hepatic impairment (Child-Pugh class B or C) must hold ibrutinib until resolved to mild impairment (Child-Pugh class A) or better, and could be retreated according to resolved hepatic conditions (ie, 280 mg for mild impairment). Monitor participants for signs of toxicity and follow dose modification guidance as needed (refer to Section 6.1.1.3). Child-Pugh Score is provided in Section 10.6, Appendix 6.

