6.5.2. Medications to be Used with Caution

6.5.2.1. Drugs That may Alter Ibrutinib Plasma Concentrations

Ibrutinib is metabolized primarily by CYP3A. Avoid coadministration with strong or moderate CYP3A inhibitors and consider alternative agents with less CYP3A inhibition. If a strong CYP3A inhibitor must be used, consider reducing the ibrutinib dose to 140 mg or withhold treatment temporarily. Participants should be monitored for signs of ibrutinib toxicity. If the benefit outweighs the risk and a moderate CYP3A inhibitor must be used, monitor participant for toxicity and follow dose modification guidance as needed. Avoid grapefruit and Seville oranges during ibrutinib treatment, as these contain moderate inhibitors of CYP3A.

Avoid concomitant use of strong CYP3A inducers (eg, carbamazepine, rifampin, phenytoin, and St. John's Wort). Consider alternative agents with less CYP3A induction.

A list of common CYP3A inhibitors and inducers is provided in Section 10.7, Appendix 7; a comprehensive list of inhibitors, inducers, and substrates may be found at <http://medicine.iupui.edu/clinpharm/ddis/table.aspx>. This website is continually revised and should be checked frequently for updates.

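### Tables 2 and 3 of the protocol: the relative restart step and the milligrams printed beside it conflict for a participant already on 280 mg ibrutinib

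*Protocol*

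**What the plan says.** The assigned dose in Section 6.1 is "Ibrutinib 420 mg (140 mg×3 capsules) orally administered daily beginning from Day 1 in Week 1".

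Section 6.1.1.3 sets the restart rules after toxicity.

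- **Table 2, second occurrence:** the participant "may restart at 1 dose level lower (ie, 280 mg/day / 2 capsules").
- **Table 2, third occurrence:** the participant "may restart at 1 dose level lower (ie, 140 mg/day / 1 capsule").
- **Table 2, footnote a (attached to the first occurrence):** on resuming, "restart at the same or lower dose based on benefit risk evaluation", and then "If the toxicity reoccurs, reduce daily dose by 140 mg".
- **Table 3, first Grade 2 cardiac failure and first Grade 3 arrhythmia:** "restart at 1 dose level lower (ie, 280 mg/day / 2 capsules"). The word *may* is absent here. The arrhythmia row carries a footnote asking for a benefit-risk evaluation before resuming. The two Grade 2 cardiac failure restart rows carry no such footnote, and no Table 3 footnote states a 140 mg step.

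Two other sections can change the current dose. For Child-Pugh class A impairment arising on study, Section 6.1.1.4 says "the recommended dose reduction for ibrutinib is to a level of 280 mg daily (2 capsules") and then refers the reader to Section 6.1.1.3 for toxicity. For a strong CYP3A inhibitor that must be used, Section 6.5.2.1 says "consider reducing the ibrutinib dose to 140 mg or withhold treatment temporarily". The text under Table 3 cross-refers to Section 6.5.2.1 without saying how the two rules combine.

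**The concern.** Each reduction row gives a relative instruction and an absolute one, and joins them with *ie* as if they were the same thing. They are the same only along the standard descent from 420 mg. For a participant who is already lower when the event occurs, the row gives two different answers.

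What is at stake is the dose at which someone resumes ibrutinib after a severe toxicity, including cardiac events. A site that follows the printed milligrams can restart at the dose being taken when the event happened. A site that follows the words reaches a lower one. Both could claim to have complied with the protocol.

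**Working it through.** **Inputs.** Starting dose 420 mg as three 140 mg capsules (Section 6.1); printed restart doses 280 mg and 140 mg (Tables 2 and 3); a step of 140 mg (Table 2 footnote a); 280 mg for Child-Pugh A (Section 6.1.1.4); 140 mg as an option with a strong CYP3A inhibitor (Section 6.5.2.1).

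**Assumption.** One dose level is taken to be one 140 mg capsule. This follows from the printed rows and footnote a.

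**Reproducing the printed figures.** 420 − 140 = 280 and 280 − 140 = 140. Both are correct for a participant who comes down from 420 mg one row at a time.

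**Comparing each printed dose with the dose at the event.** Change = printed dose − dose at event; ratio = printed dose / dose at event; relative reading = dose at event − 140.

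| Dose at event (mg) | Printed dose (mg) | Change (mg) | Ratio | Relative reading (mg) |
|---|---|---|---|---|
| 420 | 280 | −140 | 0.67 | 280 |
| 280 | 280 | 0 | 1.00 | 140 |
| 280 | 140 | −140 | 0.50 | 140 |
| 140 | 280 | +140 | 2.00 | 0 (no such level) |
| 140 | 140 | 0 | 1.00 | 0 (no such level) |

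In the rows that print 280 mg, the two readings agree only at 420 mg.

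**Routes to 280 mg before such a row applies.**

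1. *Hepatic rule.* A participant on 280 mg for Child-Pugh A is referred to Section 6.1.1.3. At a first Grade 2 cardiac failure or Grade 3 arrhythmia, Table 3 prints 280 mg: a 0 mg change, against 140 mg by the words.
2. *Footnote a.* A participant restarted at 280 mg after a first Table 2 event has a recurrence. The row's words and footnote a both give 280 − 140 = 140 mg; the row's milligrams give 280 mg.
3. *Across tables.* A participant reduced to 280 mg at a second Table 2 event then has a first Table 3 event, and 280 mg is printed again. In the other direction, a participant reduced to 280 mg under Table 3 meets the same figure in the second-occurrence row of Table 2.

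**A participant on 140 mg.** This can arise from the strong-inhibitor option, or from a full descent through one table followed by an event in the other. The printed 280 mg would then be twice the dose at the event, while the words point to a level that does not exist. These are remote combinations and add little to the case at 280 mg.

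**The case against.** The best defence is that the operative instruction is relative. Table 2 attaches the same phrase to 280 mg in one row and to 140 mg in the next, so the milligrams read naturally as stations on the 420–280–140 ladder rather than as a definition. In Table 2, footnote a supports the words, so two of the three texts agree. Resumption there is discretionary, and Section 6.6 has dose adjustments overseen by medically qualified staff. All of this stands, and it makes Table 2 resolvable for a careful reader. It does not settle Table 3, where the restart is not worded as optional, there is no stated 140 mg step, and the cardiac failure rows lack the benefit-risk note. Oversight also does not say which of two conflicting instructions is the compliant one.

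A reader might go further and infer that the protocol tells sites to double the dose after toxicity. The documents do not support that. Requiring a strong CYP3A inhibitor is an exclusion criterion (Section 5.2, criterion 13). On study such drugs are to be avoided, 140 mg is only an option to consider, and a temporary hold is the stated alternative. The site would also have to raise the dose under an instruction that says *lower*. Nor would 280 mg be an overdose, which Section 8.7 defines as more than 420 mg in a day.

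A reader might also infer that exposure and safety data in this 14-participant trial will be distorted. The documents give no frequency for any of these combinations, so that is not shown.

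**Conclusion.** The contradiction is in the text and holds in a limited form. For a participant on 280 mg at the event, the rows that print 280 mg give a reduction by their words and none by their milligrams: 140 mg against 280 mg. The protocol creates that situation by at least three routes of its own, and no section ranks the words over the figure. Table 3 is the clearest case.

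The conclusion rests on reading *ie* literally and on a dose level being 140 mg. How often it would arise cannot be estimated from the document. Severity is moderate: the point concerns consistent handling of participants after severe toxicity and does not touch the primary response-rate analysis. Which dose is right is a clinical matter and is not judged here.

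**What to change.** The sponsor's clinical team should reconcile Tables 2 and 3, Table 2 footnote a, Section 6.1.1.4 and Section 6.5.2.1, so that they give one consistent restart instruction for a participant already on a reduced dose when the event occurs. The same edit should make clear what the original dose level in the first row of Table 2 means for such a participant. No dose or dosing rule is proposed here.

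The cost is a wording change in the next amendment, with no added visits or participants.

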6.1.1.4. Dose Modification for Hepatic Impaired Participants

Ibrutinib is metabolized in the liver. For participants who develop mild liver impairment while on study (Child-Pugh class A), the recommended dose reduction for ibrutinib is to a level of 280 mg daily (2 capsules). Participants who develop moderate or severe hepatic impairment (Child-Pugh class B or C) must hold ibrutinib until resolved to mild impairment (Child-Pugh class A) or better, and could be retreated according to resolved hepatic conditions (ie, 280 mg for mild impairment). Monitor participants for signs of toxicity and follow dose modification guidance as needed (refer to Section 6.1.1.3). Child-Pugh Score is provided in Section 10.6, Appendix 6.

6.1.2. Rituximab

All participants will receive rituximab and will follow the prescribing information for rituximab dosing and toxicity management. Commercial product of rituximab at clinical sites will be used.

6.1.2.1. Dosage, Preparation, and Administration of Rituximab

The first dose of rituximab will be administered IV on Day 1 of Week 1 of the Treatment Phase and will continue to be administered at the clinical site weekly for 4 consecutive weeks, followed by a second course of once-weekly rituximab for 4 consecutive weeks after a 12-week interval (Weeks 1, 2, 3, 4, 17, 18, 19, and 20). Rituximab doses may be delayed for up to 3 days due to scheduling conflicts. Rituximab will be administered IV by clinic staff according to the prescribing information. Ibrutinib will be administered prior to rituximab infusion when given on the same day. Rituximab should not be mixed or diluted with other drugs. Rituximab will be administered as an IV infusion. Premedication will be given prior to each administration in accordance with local standard practice.

In the event of an infusion reaction, institute medical management (eg, glucocorticoids, epinephrine, bronchodilators, or oxygen) as appropriate. If hypersensitivity (nonIgE-mediated) or an infusion reaction develops, the infusion should be temporarily slowed or interrupted. The infusion can continue at one-half the previous rate upon improvement of participant symptoms. Depending on the severity of the infusion reaction and the required interventions, treatment with rituximab may be temporarily or permanently discontinued. See Section 6.1.2.2 for further instructions.

6.1.2.2. Dose Delay of Rituximab

In order to initiate a subsequent dose with rituximab, the participant must not have any unmanageable, potentially rituximab-related nonhematological toxicity that is \geq Grade 3 in severity. Any other clinically important events where dose delays may be considered appropriate by the investigator must be discussed with the Medical Monitor. If a dose is missed due to scheduling conflicts, it can be delayed up to 3 days after the scheduled time. If dosing must be delayed for >3 days for reasons other than toxicity, contact the Medical Monitor. Rituximab may be withheld for a maximum of 28 consecutive days for toxicity. Rituximab should be discontinued in the event of a rituximab toxicity lasting >28 days, unless reviewed and approved by the Medical Monitor. Even if rituximab infusion is delayed due to scheduling conflicts, ibrutinib dosing should continue.

6.1.2.3. Dose Interruption of Rituximab

Modify administration of rituximab for infusion-related reactions of any severity.

- For Grades 1 and 2 infusion-related reactions, slow the infusion rate by a minimum of 50% and monitor participant closely. Provide medical intervention as indicated. If symptoms resolve, complete the infusion at the decreased rate. If symptoms do not improve, or worsen, discontinue the infusion.
- For Grade 3 infusion-related reactions, interrupt the infusion, provide medical intervention as appropriate. Monitor participant closely and if symptoms resolve resume the infusion at 50% or less of the previous rate. If there is no return of symptoms, complete the infusion at the decreased rate. If symptoms do not improve or worsen, discontinue the infusion.
- For Grade 4 infusion-related reactions, stop the infusion. Provide appropriate medical intervention. Contact the Medical Monitor prior to rechallenge or if permanent discontinuation of rituximab is necessary.

6.1.2.4. Dose Modification of Rituximab

The dose of rituximab should be modified according to the dose modification guidelines in [Table 4](#) if either of the following toxicities occur: Any Grade 4 or unmanageable Grade 3 nonhematologic toxicity attributed to rituximab.

Table 4: Dose Modification for Rituximab Toxicity

Occurrence	Action to be Taken
First to Third	Withhold rituximab until recovery to Grade ≤ 1 or baseline; may restart at original dose level
Fourth	Discontinue rituximab ^a

^a If rituximab is discontinued for toxicity, participant may continue ibrutinib.

6.1.2.5. Rituximab Associated Tumor Flare (IgM Flare)

Plasmapheresis may be indicated before or during the initial rituximab therapy to avoid or to manage tumor flare-related complications such as hyperviscosity (see [Section 5.3 Lifestyle Considerations](#)). Therapy with rituximab is commonly associated with a surge of IgM levels (tumor flare). This initial transient increase of IgM levels mostly does not indicate disease progression at treatment initiation and participants may continue therapy with rituximab. The occurrence of rituximab associated tumor flare should be recorded as an AE (refer to [Section 8.5.1.1](#)). If necessary additional laboratory tests, physical examinations, and in the case of previous lymphadenopathy or splenomegaly, computed tomography (CT) scans might be performed to discriminate tumor flare from disease progression.

6.1.2.6. Criteria for Permanent Discontinuation of Study Intervention

Investigators are encouraged to keep a participant who is experiencing clinical benefit in the study unless confirmed disease progression, significant toxicity puts the participant at risk, or routine noncompliance puts the study outcomes at risk. For a complete list of criteria for permanent

discontinuation of study intervention, refer to Section 7.1, Discontinuation of Study Intervention. An EOT visit is required for all participants except for those who have withdrawn full consent.

6.2. Preparation/Handling/Storage/Accountability

Preparation/Handling/Storage

Ibrutinib will be manufactured and provided under the responsibility of the sponsor. Refer to the IB for a list of excipients.¹⁶

Ibrutinib capsules, 140 mg should be stored according to the storage conditions indicated on the label. The recommended storage condition for ibrutinib capsules is 15°C to 25°C with excursions permitted to 30°C.¹⁶ Clinical sites may use scanning technology to manage clinical trial supplies and drug compliance activities.

For a definition of ibrutinib overdose, refer to Section 8.7, Treatment of Overdose.

Refer to the pharmacy manual/study site investigational product and procedures manual for additional guidance on ibrutinib preparation, handling, and storage.

Rituximab vials should be stored refrigerated between 2°C to 8°C. Vials should be protected from light. Do not freeze or shake. Investigators should refer to the current rituximab package insert for additional guidance.²⁹

Accountability

The investigator is responsible for ensuring that all study intervention received at the site is inventoried and accounted for throughout the study. The dispensing of ibrutinib to the participant, and the return of ibrutinib from the participant (if applicable), must be documented on the intervention accountability form. Participants must be instructed to return all original containers, whether empty or containing ibrutinib. Ibrutinib administered to the participant must be documented on the intervention accountability form. Ibrutinib will be stored and disposed of according to the sponsor's instructions. Study-site personnel must not combine contents of the study intervention containers.

Ibrutinib must be handled in strict accordance with the protocol and the container label and must be stored at the study site in a limited-access area or in a locked cabinet under appropriate environmental conditions. Unused ibrutinib, and ibrutinib returned by the participant, must be available for verification by the sponsor's study site monitor during on-site monitoring visits. The return to the sponsor of unused ibrutinib or used ibrutinib for destruction, will be documented on the intervention return form. When the study site is an authorized destruction unit and ibrutinib supplies are destroyed on-site, this must also be documented on the intervention return form.

Ibrutinib should be dispensed under the supervision of the investigator or a qualified member of the study-site personnel, or by a hospital/clinic pharmacist. Ibrutinib will be supplied only to participants participating in the study. Returned ibrutinib must not be dispensed again, even to the same participant. Whenever a participant brings his or her ibrutinib to the study site for capsule

count, this is not seen as a return of supplies. Ibrutinib may not be relabeled or reassigned for use by other participants. The investigator agrees neither to dispense the study intervention from, nor store it at, any site other than the study sites agreed upon with the sponsor. Further guidance and information for the final disposition of unused ibrutinib are provided in the Study Reference Manual.

